# 5. - Every 12 weeks until disease progression

- ECG
- LVEF

# d) End of treatment - Safety visit (after 28 days of end of treatment)

Safety visit will be performed at day 28±4d after the end of treatment to determine patient general status and clearly identify adverse events that persists and could be related to study drug. After this visit, only SAEs that could be related to study drug should be expedited reported to the Sponsor.

- Physical examination
- Vital signs
- ECOG performance status
- Neurologic examination and Modified Barthel Index
- Ophthalmologic anamnesis and evaluation by Oncologist (if there's any alarm symptom or sign, patient will be evaluated by Ophthalmologist)
- ECG

- Adverse events follow-up
- Concomitant medications
- Haematology, coagulation, serum biochemistry,
- Pregnancy test (urine test and in case this test be positive, a serum pregnancy test should be done to confirm no pregnancy.

# e) Follow-up before progression disease

- ECOG performance status
- Neurologic examination and Modified Barthel Index
- Haematology, coagulation, serum biochemistry, and pregnancy test (urine test and in case this test be positive, a serum pregnancy test should be done to confirm no pregnancy.), (only if patient it's on treatment)
- CT Scan (every two months up to 12 months, thereafter patients will be assessed as per institutional criteria)
- Contrast enhanced brain MRI (every two months up to 12 months, thereafter patients will be assessed as per institutional criteria)
- Colour Digital Photography (including a metric ruler) of the skin lesions (every two months up to 12 months, thereafter patients will be assessed as per institutional criteria).

After one year of 1st day of treatment, follow up will be performed according local normal practise.

f) Follow-up before progression disease after ending treatment:

- Subjects who no longer receive study treatment due to progression should remain in follow-up until their death or until the closure of the study (whichever comes first).
- Subjects who no longer receive study treatment due to unacceptable toxicity or at the discretion of the investigator should remain in follow up until progression. Visits will be scheduled every 8 weeks and tumor evaluation should be performed every 8 weeks until tumor progression the fist year, and after 12 months, the tumor evaluation can be done as per institutional criteria. The tests and questionnaires can be done according to the normal practise too.
- Subjects who have switched to an alternative treatment do not perform a formal follow-up, except to record the date of the death.

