# 8. STUDY ASSESSMENTS

# 8.1. Schedule for tests and determinations

Table 11. Schedule for tests and determinations

Visit	Baseline (D-28 to D-1)	w4	w8 (D-56)	Every 4w	Every 8w	Every 12 w	End of treatment (28 +/-4d)	FU before DP	FU after DP for OS
Informed consent	Х								
Screening registration	Х								
Histology confirmation of disease	Х								
BRAF Status	×								
Anamnesis	Х								
Demographics	Х								
Physical examination / vital signs	х	Х	х	Х			Х		
ECOG PS	×	Х	х	Х			X	Х	
Basic neurologic examination and Modified Barthel Index	Х	Х	X	Х			X	×	
Ophthalmologic anamnesis an evaluation by Oncologist	Х	X	X	Х			X		
Ophthalmologist exploration	If clinical suspicion								
ECG	×	Х				Х	×		
LVEF (as per institutional guidelines)	X					Х			
Concomitant medications	×	Х	Х	Х			Х		
Inclusion/exclusion criteria	×								
QoL	×	X at weeks 8 and 24							
Analytical tests									
Clinical laboratory test	×	Х	Х	Х			X	Х	
Pregnancy test	Х			Х			×		
Disease evaluation									
Abdominopelvic CT Scan (1)	Х		Х		X (³)			X (every 8w) (³)	
Brain MRI (  )	х		Х		X (³)			X (every 8w) (³)	

Colour Digital Photography (including a metric ruler) of skin lesions (¹)	х		Х		X (³)			X (every 8w) (³)	
Safety evaluation									
Adverse events and Serious Adverse events		Every 4 weeks throughout all the study (From ICF signature up to EoT visit)							
Study Treatment									
COMBO450 follow-up and dispensing		Х		х					
Dose reduction		Throughout all the study, when applicable							
Dose delay		Throughout all the study, when applicable							
Long term FU									
OS Follow-up									Х
New anti-cancer therapy									Х

 $(^1)$  Out of the assessments indicated by protocol, patients can be assessed whenever the investigator considers it indicated.

 Contrast enhanced MRI.

 $(^3)$  Assessments will be done every two months up to 12 months, thereafter, patients will be assessed as per institutional criteria.

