#### Non-radiological Assessments

Visible cutaneous lesions must be measured clinically. Digital and standardized photographic images including a ruler for scale as part of the image are recommended for documentation. All clinical assessments must be performed within proximity (± 7 days) of any protocol specified radiographic assessments

**Safety evaluation:** Safety assessments and adverse events include tumour-related, unrelated and treatment-related signs and symptoms. Adverse events will be documented and recorded in the CRF upon patient notification. AEs will be collected from the signing of Informed Consent until the end of treatment visit (30 days after end of treatment) or up to resolution. Classification of toxicity will be done according to the common terminology criteria for adverse events of the National Cancer Institute, version 4.03 (NCI CTCAE v. 4.03).

**PFS follow-up:** Body CT-scan and contrast enhanced brain MRI will be performed baseline and every 8 weeks (+/-1 week) up to 12 months and according to normal practice thereafter **until disease progression**, **independently of the end of treatment reason if it was not the documentation of disease progression**.

**OS Follow-up:** After disease progression all patients will be monitored to determine subsequent antineoplastic treatments and survival. It is recommended to maintain contacts by phone or by other methods every 4 weeks to carry out timely follow-up (up to 24 months or study closure).

**New anti-cancer therapy:** Information on subsequent treatments should include the list of post-treatment treatments, the drugs administered, and the date of initiation and discontinuation of each drug. All data will be recorded in the medical record and in the eCRF.

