# 4.6. INTRACRANIAL PROGRESSION-FREE SURVIVAL (IPFS).

Intracranial Progression-free survival (PFS), defined as the time from inclusion (first dose of treatment) until intracranial tumour progression (RECIST 1.1) or death. Patients without any of the previous events are censored at the date of the last available tumor assessment.

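### Patients who stop study drug without progression and then switch therapy fall under two conflicting follow-up rules, and a switch before progression made more than about 30 days after the last dose has no scheduled collection point

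*Combined protocol and SAP*

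**What the plan says.** **Scanning after treatment ends.** The PFS follow-up paragraph of protocol 8.1 sets body CT and brain MRI "every 8 weeks (+/-1 week) up to 12 months and according to normal practice thereafter", continuing to progression "independently of the end of treatment reason if it was not the documentation of disease progression". It makes no exception for a new therapy.

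**The list in 8.2 f).** Its heading is "Follow-up before progression disease after ending treatment".
- The first bullet covers patients who stopped because of progression; they are followed to death or study closure.
- The second agrees with 8.1: patients who stopped "due to unacceptable toxicity or at the discretion of the investigator should remain in follow up until progression", with 8-weekly tumour evaluation in the first year and institutional practice afterwards.
- The third reads: "Subjects who have switched to an alternative treatment do not perform a formal follow-up, except to record the date of the death". It carries no condition on progression status.

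**Recording the new therapy.** Section 8.1 states: "Information on subsequent treatments should include the list of post-treatment treatments, the drugs administered, and the date of initiation and discontinuation of each drug". No timing limit is given. In Table 11 the row "New anti-cancer therapy" is marked only in the last column, for survival follow-up after progression. The OS follow-up paragraph of 8.1 likewise places subsequent treatments after progression, and 8.2 g) lists the item under long-term survival follow-up. The pre-progression list in 8.2 e) does not contain it.

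**Analysis.** SAP 4.6 (iPFS) and 4.7 (ePFS) count progression or death as the event. For everyone else: "Patients without any of the previous events are censored at the date of the last available tumor assessment". Neither these sections nor protocol 10.2 says how a new therapy started before progression is handled.

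**The concern.** The protocol itself makes this situation foreseeable. Table 10 contains several permanent-discontinuation rules for toxicity, and section 7.3.3 requires study drug to stop if other anticancer therapy is needed. Some patients will therefore leave treatment without progression and may start something else.

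For such a patient the second and third bullets of 8.2 f) both apply, and no precedence is stated. Whether a progression after the switch reaches the database then depends on which instruction the site follows. The endpoints exposed are iPFS, ePFS, iDOR in responders, and the percentages free of progression at fixed times. Without the date of the new therapy, the analyst cannot tell progression on study drug from progression on a later drug, or test how much the choice matters.

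**Working it through.** No figure in the plan depends on this point. The sample size (38 evaluable, 48 enrolled in cohort 1) is for response before local treatment. The check is a comparison of the rules, followed by a worked patient and a scale calculation.

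**1. Do the rules overlap?** Section 8.1 and the second bullet of 8.2 f) select on why study drug stopped. The third bullet selects on whether another therapy was started. These conditions are not exclusive, so a patient who stops for toxicity and then switches meets both. One rule says scan to progression; the other says record death only.

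**2. Is the switch date collected?**
- *Within about 30 days of the last dose:* probably yes. Section 7.3 records medications to 30 days after the last protocol treatment, and the visit in 8.2 d), at day 28 ± 4, asks for concomitant medications.
- *Later, before progression:* section 8.1 asks for drug dates in general terms, but Table 11, 8.2 e) and 8.2 g) assign no visit at which to obtain them.
- *After progression:* yes, through Table 11 and 8.2 g).

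**3. An invented patient.** The protocol equates week 24 with 6 months, so 4 weeks count as one month here. Suppose response is seen at month 2 (week 8), the last scan on drug is at month 4 (week 16), and the patient then stops for toxicity and switches. Suppose intracranial progression would be seen at month 6 (week 24) and death from melanoma occurs at month 14. Under the third bullet, assume no outside scan is entered.

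| Quantity | Scans continue (8.1) | Death only (8.2 f), third bullet) |
|---|---|---|
| iPFS | 6 months, progression | 14 months, death |
| Unscanned time before the event | none beyond the 8-week interval | 14 − 4 = 10 months |
| Status at 12 months | progressed | progression-free |
| iDOR | 6 − 2 = 4 months | 14 − 2 = 12 months |
| iPFS if still alive at month 14 | 6 months, progression | censored at month 4 (SAP 4.6) |

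The same logic gives ePFS if the progression is extracranial. When the patient dies, progression-free time is too long. When the patient lives, the SAP rule censors at the last scan, so time is lost rather than added.

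**4. Scale (assumed rates).** Planned N = 48 + 15 = 63.
- Switchers before progression: 0.05 × 63 = 3.2; 0.10 × 63 = 6.3; 0.20 × 63 = 12.6. That is about 3, 6 or 13 patients.
- Weight of one patient in a crude percentage: 1/63 = 1.6 points overall; 1/48 = 2.1 in cohort 1; 1/15 = 6.7 in cohort 2. A Kaplan-Meier estimate moves by a similar but not identical amount.

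**5. When it matters most.** After 12 months both rules leave imaging to local practice, so the difference in scheduled scans is clearest for switches in the first year.

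**The case against.** The best reply is that this is loose drafting rather than a true contradiction. Section 8.1 speaks to why study drug stopped, not to what happens after another drug starts, so the third bullet could be a specific exception. It could also be meant for patients who have already progressed: the first bullet shows that the heading of 8.2 f) is not a reliable guide, and section 5.3 follows progressed patients for survival only.

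The ambiguity is fair, and that sites would act differently is an inference. But neither reading clears the text. As an exception, the bullet removes the scans that the PFS endpoints need, and no analysis rule is given for the result. As a post-progression rule, its death-only instruction conflicts with 8.1, 8.2 g) and Table 11, which collect subsequent therapy after progression.

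Three stronger inferences are tempting, and the documents do not support them:
- *That switchers cannot be identified at all.* The new-therapy paragraph of 8.1 has no timing limit, early switches can be captured as concomitant medication, and the SAP listings carry end-of-treatment reasons (3.5) and the dates of end of treatment, progression and death (4.4). What lacks a scheduled source is the date of a later switch.
- *That iPFS and ePFS are always inflated.* This holds for patients who die without recorded progression. Living switchers are censored at the last scan under SAP 4.6 and 4.7.
- *That the primary result is at risk.* Response at day 56, before local treatment, is essentially settled before this problem arises.

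**Conclusion.** The inconsistency is real and should be corrected. A patient who stops without progression and then switches is subject to scanning until progression under 8.1 and the second bullet of 8.2 f), and to death-only recording under the third bullet. Following the third bullet can replace an observed progression with a later death; in the worked patient iPFS moves from 6 to 14 months and the 12-month status reverses. The date of a switch before progression, if later than about 30 days after the last dose, has no scheduled collection point.

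The effect is confined to secondary, single-arm endpoints: iPFS, ePFS, iDOR and the landmark percentages. Its size cannot be established from the documents, which give no switch rate. The range of about 3 to 13 patients rests wholly on the assumed 5% to 20%, and the worked patient is illustrative. The weight of 6.7 points per patient applies to cohort 2, which the plan calls exploratory.

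**What to change.** 1. **Protocol 8.2 f), third bullet.** Reconcile it with 8.1. Patients who switch before documented progression stay on the tumour-assessment schedule that 8.1 already sets, for endpoint ascertainment. For progressed patients, refer to the OS follow-up in 8.1 and 8.2 g), covering survival and subsequent therapy. Merely limiting the bullet to progressed patients would leave it asking for death alone, against those sections.
2. **Table 11 and 8.2 e)/f).** Mark new anti-cancer therapy in the FU before DP column and add it to the pre-progression lists, so that its start date has a collection visit.
3. **SAP 4.6 and 4.7.** State how new therapy before progression is handled. The two candidates are using all scans to progression and censoring at the last scan before the new therapy. The sponsor should choose one as the main analysis and report the other as a sensitivity analysis.
4. **If the data are already locked.** SAP 3.5 speaks of database closure, so wording changes may come too late to recover scans that were never done. In that case, query sites for switch dates before progression and any available scans, and report how many patients are affected and which follow-up rule was applied.

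The cost is a few extra data entries or site queries and one additional table. No imaging is added beyond what 8.1 already schedules.

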# g) OS Long term follow-up

New anticancer therapy

Follow-up after disease progression will be made according to local practice. Survival information may be obtained via telephone contact with the patient, patient's family or by contact with the patient's current physician. Survival data will be collected up to the time of the final overall survival (OS) analysis. At this point Investigators will be notified that no further data collection for the study is required.

The status of ongoing, withdrawn (from the study) and lost to follow up patients at the time of an overall survival analysis should be obtained by the site personnel by checking the patient notes,

hospital records, contacting the patient's general practitioner and checking publicly available death registries.

# 8.3. Study timetable and end of study

- Expected recruitment period: 36 months
- Expected follow-up: 24 months

# 8.3.1. End of Study Declaration

Last Patient Last Visit, expected on 1Q 2024. The study will be considered closed from a normative point of view after data on primary and secondary variables are sufficiently prepared for its initial publication.

# 8.3.2. Early study termination

This study can be terminated prematurely if in the opinion of the sponsor there is a reasonable and sufficient cause. The investigator will receive a written notification in which the sponsor motivates the interruption of the study.

Reasonsthat justify are as follows, but not limited to:

- Finding of unforeseen, considerable or unacceptable risks for the patients.
- Impossibility to include an acceptable number of patients.
- Insufficient compliance with protocol requisites.
- Plans to modify, halt or discontinue the development of study drug.
- In case of early termination of the study, all the study material must be returned to Sponsor.

# 9. Assessment of Safety

The safety population (SP) consists of all enrolled subjects who received at least one dose of study treatment. Patients will be monitored for safety during all stages of the study. All safety and tolerability assessments will be done at pre-dose unless otherwise specified.

Assessment of adverse events, safety, and toxicity will be performed according to the National Cancer Institute Common Toxicity Criteria (version 4.03) from the time of Informed Consent for the pre-registration phase until the end of study. The safety of study treatment will be assessed through the recording, reporting and analysing of baseline medical conditions, adverse events, and physical examination findings including vital signs, ECGs and laboratory tests.

# 9.1. Safety Parameters

# 9.1.1. Demographic/Medical History

All clinically relevant demographic and medical history data will be obtained from all patients enrolled in the study, by the investigator or qualified designee. Medical history will include all active conditions, and any condition diagnosed that are considered clinically significant by the Investigator. Melanoma history will be recorded separately and not listed as Medical History.

#### 9.1.2. Prior Medications

The investigator or qualified designee will review prior medication use, including any protocol-specified washout requirement, and record prior medication taken by the subject within 30 days before starting the trial. Prior treatments for melanoma will be recorded.

# 9.1.3. Vital Signs

The investigator or qualified designee will take vital signs at screening, prior to the administration of COMBO 450 and as specified in the Table of Schedule of Assessments. Vital signs include temperature, pulse, respiratory rate, weight and blood pressure (after sitting for 5 minutes). Height will be measured at screening only.

# 9.1.4. Physical Examination

A standard physical examination will be performed to all patients treated with COMBO 450 as specified in the Table of Schedule of Assessments.

#### 9.1.5. Electrocardiogram (ECG)

A standard 12-lead ECG will be performed using local standard procedures once at baseline and as specified in the Table of Schedule of Assessments. Clinically significant abnormal findings should be recorded as medical history.

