- After progression, patients will be followed only for overall survival.
  - o In case of encorafenib and binimetinib are providing a clinical benefit to any patient, treatment could be continued after discussion with Sponsor if it agrees on that. In this case, follow up will be done as per institutional criteria. In the study, these patients will be followed only for overall survival.
- Study assessments: in each monthly visit, adverse events will be registered, blood samples will be collected for blood cell counts and general biochemistry (including magnesium, potassium and creatinine-kinases); an ECG will be performed at baseline, after one month of treatment, and every 3 months thereafter; a left ventricular ejection fraction (LVEF) evaluation will be performed by as per institutional guidelines at baseline and every 3 months thereafter ophthalmologic anamnesis and evaluation will be performed by oncologist at baseline and in every monthly visit, if there's any alarm symptom or sign, patient will be evaluated by Ophthalmologist. Body CT-scan and contrast enhanced brain MRI will be performed baseline and every 8 weeks up to 12 months and according to normal practise thereafter. More information regarding study determination is provided in section 8 of this protocol.

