# **Protocol specifications for trial determinations**

**Informed Consent Form (ICF):** Determinations performed by routine clinical practice before signing the informed consent will be valid, provided they are carried out following from this protocol, if they have been performed during the period included in the table 11.

**Screening registration:** Any patient that sign ICF should be registered in the EDC system and have assigned a unique screening number.

**Anamnesis:** to be performed during the baseline period in the 2 weeks prior to inclusion. Medical history will include all active conditions and any condition diagnosed considered to be clinically significant by the investigator. Melanoma history will be recorded separately and not listed as Medical History.

**Demographics:** Date of birth, race, and sex.

**Physical examination/vital signs:** Complete physical examination, weight, height, and vital signs (pulse, respiratory rate, **blood pressure** and body temperature).

**ECOG-PS:** Functional status will be assessed using the ECOG score.

**Neurological examination:** Basic neurological assessment according to normal practice and Modified Barthel Index according to "Guidelines for the Modified Barthel Index of Activities of Daily Living"

**Ophthalmologic anamnesis and evaluation by Oncologist:** ophthalmologic anamnesis and evaluation performed by oncologist as a part of physical examination and it will be performed at baseline and in every monthly visit. Only if there's any alarm symptom or sign or previous ocular antecedents, patient will be evaluated by Ophthalmologist.

**Ophthalmologist examination:** Patient will be evaluated by Ophthalmologist if there's any alarm symptom or sign or previous ocular antecedents.

**ECG:** Standard 12-lead ECG at baseline, after 4 weeks of treatment, after every 12 weeks and in the end of treatment visit. Additional ECGs may be performed at the discretion of the investigator.

**Concomitant medication:** All drugs taken within 30 days before starting the trial and concomitantly during the study will be recorded in medical records and in eCRF with indication, dose information and administration dates.

**Inclusion and Exclusion Criteria:** Verification that patients meet all inclusion criteria and none of exclusion.

Quality of Life: EORTC QLQ 30 administered at baseline, at week 8 and week 24.

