#### 9.2.1.1. Adverse Event (AE)

An AE is defined as any untoward medical occurrence in a patient or clinical investigation subject administered a pharmaceutical product and which does not necessarily have to have a causal relationship with this treatment. An adverse event (AE) can therefore be any unfavourable and unintended sign (including an abnormal laboratory finding, for example), symptom, or disease temporally associated with the use of a medicinal product, whether considered related to the medicinal product.

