# 9.3. Assessment

All assessments of AEs (serious and non-serious) listed below should be recorded on the Adverse Event page of the CRF/eCRF or in the SAE form as appropriate.

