# 9.4. Reporting

# 9.4.1. Reporting an Adverse Event

Adverse events (serious and non-serious) spontaneously reported by the patient and/or in response to an open question from the study personnel or revealed by observation will be recorded during the study at the investigational site. Information about AEs (including SAEs) will be collected from the signing of Informed Consent at least until the end of treatment visit or up to resolution. For each AE, the investigator will evaluate and report the onset (date and time), resolution (date and time), severity, causality, action taken, outcome, and whether it caused the patient to discontinue the study.

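### Section 9.1.5 sends clinically significant ECG abnormalities to medical history without limiting this to baseline, which contradicts the adverse-event rules for on-treatment ECGs

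*Combined protocol and SAP*

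**What the plan says.** Section 9.1.5 has two sentences. The first sets the scope: "A standard 12-lead ECG will be performed using local standard procedures once at baseline and as specified in the Table of Schedule of Assessments". The second is the recording rule: "Clinically significant abnormal findings should be recorded as medical history". Nothing limits the second sentence to tracings taken before the first dose.

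**Schedule.** Under section 5.3, "an ECG will be performed at baseline, after one month of treatment, and every 3 months thereafter". Table 11, the determinations text that follows it and section 8.2 add an ECG at the end-of-treatment safety visit.

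**Adverse events.** Under section 9.2.1.1 an adverse event "can therefore be any unfavourable and unintended sign". Section 9.3 says that assessments of adverse events "should be recorded on the Adverse Event page of the CRF/eCRF". Under section 9.4.1, events "revealed by observation will be recorded during the study at the investigational site", and collection runs from informed consent to at least the end-of-treatment visit. Section 10.4 asks for all adverse events to be recorded by CTCAE v4.03 at each visit. Section 10.6 defines treatment-emergent events by a start after study treatment. Both toxicity endpoints in section 10.2 include ECG changes.

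**Medical history.** Section 9.1.1 covers active conditions and diagnosed conditions that the investigator judges clinically significant, and gives no cut-off date. The determinations text in section 8.1 places medical history under anamnesis, "to be performed during the baseline period in the 2 weeks prior to inclusion".

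**QTc.** Exclusion criterion 9 uses a triplicate average baseline QTc above 500 ms and names no correction. The re-escalation rule in section 7.2.1 and the QTc rows of Table 10 use QTcF. Table 10 also uses the change from a pre-treatment value, with a cut at 60 ms.

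**The concern.** A site that sees a new, clinically significant ECG abnormality at week 4 has two instructions. The general rules make it an adverse event, with a grade and a causality assessment. Section 9.1.5, the only recording instruction specific to ECGs, makes it medical history, with neither. The neighbouring sections on vital signs, physical examination and laboratory tests carry no such sentence.

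Toxicity before and after local treatment is a secondary objective, and ECG change is a named part of it. With 21 sites, the same finding could be a graded event at one and an ungraded history entry at another. The abnormalities most exposed are those that lead to no dose change, because nothing else then prompts an adverse-event entry.

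The QTc wording raises a smaller issue. Table 10 uses the change from the pre-treatment value to choose between withholding treatment and resuming at a reduced encorafenib dose, and stopping both drugs permanently. That reference should be one defined number, and the documents do not say which one it is.

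**Working it through.** No sample size, power or error rate is involved, so the check sets the texts side by side.

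**1. How much of section 9.1.5's scope is after the first dose?** Take a patient treated for 48 weeks. The ECGs are baseline, week 4, every 12 weeks, and the end-of-treatment visit (Table 11, section 8.2).
- Counting 12 weeks from week 4 gives weeks 16, 28 and 40: 1 + 1 + 3 + 1 = 6 ECGs, 5 of them after the first dose.
- Counting from the start of treatment gives weeks 12, 24, 36 and 48: 1 + 1 + 4 + 1 = 7 ECGs, 6 of them after the first dose.

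On either count only one scheduled ECG precedes treatment. The visit within 7 days before day 1 (section 8.2) lists no ECG.

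**2. Where does each text send a new, clinically significant abnormality at week 4?**

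| Text | Destination |
|---|---|
| 9.1.5, second sentence | Medical history |
| 9.2.1.1 | Adverse event: an unfavourable, unintended sign after drug exposure |
| 9.3, 9.4.1 | Adverse event page, with severity and causality |
| 10.4 | CTCAE v4.03 record at the visit |
| 10.6 | Treatment-emergent event, by start date |
| Table 10, if QTcF exceeds 500 ms | Treatment-related adverse event with a dose action |

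Section 9.1.5 stands alone against the rest. No sentence in the protocol settles the conflict for ECGs.

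**3. What would a literal reader's entry miss?** The tables of section 10.6 and the safety shells in SAP section 5 are built from adverse events, toxicities and serious adverse events. A medical-history entry reaches none of them. The SAP shells show no ECG table. SAP table numbers 131 and 137 to 145 do not appear in the available text, so an ECG table elsewhere cannot be ruled out.

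**4. What would still be captured?** Section 10.7 presents individual and summary ECG parameters and lists clinically significant abnormal values. Section 10.2 names ECG changes beside adverse events, so a change could enter the toxicity endpoints from the ECG data. A QTcF above 500 ms triggers a Table 10 action and would probably be recorded as an adverse event for that reason.

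**5. Unit of effect.** One patient is 1/63 = 1.6 percentage points of the planned total, 1/48 = 2.1 in cohort 1 and 1/15 = 6.7 in cohort 2. These convert one patient into a rate. They do not estimate how many patients would be affected.

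**6. The QTc reference.** The Table 10 action switches at a baseline equal to the on-treatment QTcF minus 60 ms: 501 − 60 = 441, 510 − 60 = 450, 530 − 60 = 470 ms. A baseline below that line means a change above 60 ms and a permanent stop. At or above it, the patient can resume at a reduced encorafenib dose. A single tracing and a three-tracing average lead to different actions only if they fall on opposite sides of the line. How often that happens cannot be derived from the documents.

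**The case against.** The best defence is that the sentence was meant for baseline. Anamnesis appears only in the baseline column of Table 11, and medical history only among the baseline assessments of section 8.2. Section 9 lists the safety sources as "recording, reporting and analysing of baseline medical conditions, adverse events, and physical examination findings including vital signs, ECGs and laboratory tests", which separates baseline conditions from adverse events. The general adverse-event rules are explicit and apply to any sign. Many sites would read section 9.1.5 this way, and section 10.7 keeps the ECG data visible whatever page a site uses.

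Most of this stands, and it limits the consequence. It does not remove the contradiction. The first sentence of section 9.1.5 reaches past baseline, the second has no pre-dose limit, and section 9.1.1 defines medical history without a cut-off date. A listing of abnormal values is also not a graded, causality-assessed adverse event.

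On QTc, a reader might infer that one baseline ECG contradicts a triplicate average. The documents do not support that: a single baseline session can contain three tracings. Only an ambiguity remains, about the correction used and about which value Table 10 takes as its reference.

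**Conclusion.** Section 9.1.5 is wrong as written for on-treatment ECGs. It contradicts the adverse-event definition, the recording rules and the treatment-emergent definition. Under the literal reading, a new on-treatment abnormality with no dose change would be missing from the adverse-event tables.

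A reader might go further and infer that on-treatment ECG toxicity will be lost or systematically under-reported. The documents do not support this. The competing rules remain in force, ECG values are tabulated and listed separately, and QTcF events above 500 ms have their own route through Table 10. The supported conclusion is a risk of misclassification and of differences between sites, of unknown frequency. It rests on the assumption that at least some sites follow the sentence specific to ECGs over the general rules.

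The intracranial response endpoint, the sample size and the decision rule are untouched. The correction is worth making because it is cheap and concerns a named component of the safety endpoints. The QTc point is a minor clarification.

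**What to change.** **Section 9.1.5.** Replace the second sentence with a rule in two parts:
- Clinically significant ECG abnormalities already present at baseline, as pre-existing conditions, are recorded as medical history.
- Any that are new or worsened after informed consent, including on all on-treatment ECGs, are recorded as adverse events graded by CTCAE v4.03.

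The dividing point should be consent and not the first dose. Adverse events are collected from consent, so a rule sending every pre-dose finding to medical history would create a new conflict for abnormalities that arise between consent and day 1.

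**Exclusion criterion 9 and Table 10 (minor).** Name QTcF in the criterion, keep the triplicate average, and state that this same baseline QTcF is the pre-treatment value in Table 10. Dropping the triplicate average would be simpler, but it would put a single, noisier tracing behind the rule that decides permanent discontinuation.

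**Cost.** Wording only. Taking three tracings at the baseline session is already implied by the exclusion criterion. A site that now takes one would need two more per patient at that session.
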